**Evaluating the Effect of Preoperative Patient Education
on Postoperative Opioid Consumption, Storage, and
Disposal after Urogynecologic Procedures**

Protocol ID: 2017-11833

Study Protocol and Statistical Analysis Plan
06/04/2018

| | |
|--|---|
| Upload this completed narrative and any supplemental documentation to the IRB Application . | IRB USE ONLY: HS#: 2017-4003 |
| Lead Researcher Name: [name] MD | |
| Study Title: Evaluating the Effect of Preoperative Patient Education on Postoperative Opioid Consumption, Storage, and Disposal after Urogynecologic Procedures | |

CLINICAL TRIAL MASTER PROTOCOL AND INVESTIGATIONAL BROCHURE INFORMATION

| | Master Protocol | Investigator Brochure: | Investigator Brochure: | Sponsor Consent Form Template(s) |
|--|-----------------|------------------------|------------------------|----------------------------------|
| Version #: | | | | |
| Version Date: | | | | |
|  This study is investigator-authored (investigator developed the study and is conducting the study at UCI and/or with other non-UCI sites). | | | | |

NON-TECHNICAL SUMMARY

| |
|--|
| Provide a brief non-technical summary or synopsis of the study that can be understood by IRB members with varied research backgrounds, including non-scientists and non-affiliated members. |
| 
The purpose of this study is to evaluate whether providing patients with specialized preoperative counseling about the risks associated with opioid medications will lead to a reduction of opioid consumption after common urogynecologic surgeries. The study will be a randomized controlled trial that will be performed at two sites (UC Irvine Medical Center and Kaiser Permanente Orange County – Irvine Medical Center). Patients who agree to participate will be randomized to control (standard of care) arm or an intervention (specialized opioid education in the form of patient pamphlets and verbal scripts, which will be performed prior to their surgery and at the 2 week postoperative clinic visit) arm. The randomization will be stratified by medical facility. Assessment of the patients’ opioid consumption will be conducted through physician-mediated pill counts during the patients’ standardized postoperative clinic visits. Any additional opioid prescriptions within 12 months of the surgery will be evaluated by reviewing the patients’ UC Irvine electronic medical records as well as the California
 |

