Study design, identifying potential study participants, finalizing informed consent (reviewing, answering/asking questions, confirming competency, as necessary, and signing/confirming the informed consent), providing standardized patient education about opioid medications, administering patient questionnaires, and quantifying remaining postoperative opioid tablets.

[name] is a Female Pelvic and Reconstructive Surgery fellow at UC Irvine. She completed her obstetrics and gynecology residency at Johns Hopkins University. She is an author on six scientific manuscripts in the literature to date, including four manuscripts as the first author.

Research Personnel:

Name and Degree: [name]

Position/Title and Department: Junior Specialist, Obstetrics & Gynecology

Research Assistant, Obstetrics & Gynecology Department

Team Member will: Screen/Recruit Finalize Informed Consent

Perform Research Activities Access subject identifiable data

List the research activities/procedures to be performed and the individual's relevant qualifications (training, experience):

Administering patient questionnaires and quantifying remaining postoperative opioid tablets.

[name] is a research assistant within the department of Obstetrics and Gynecology at UC Irvine Medical Center. She graduated from UC Berkeley in 2017 and is in the process of applying to medical school.

SECTION 3: SUBJECT POPULATION(S) (INDIVIDUALS/RECORDS/SPECIMENS)

A. Subjects To Be Enrolled on this UCI protocol (Persons/Records/Biospecimens)

1. Complete the table of subject enrollments below.
2. If the study involves the use of existing records or biological specimens, specify the maximum number to be reviewed/collected and the number needed to address the research question.

| Category/Group (e.g., adults, controls, parents, children) | Age Range (e.g., 7-12, 13–17, adults) | Maximum Number to be Consented or Reviewed/Collected (include withdrawals and screen failures) | Number Expected to Complete the Study or Needed to Address the Research Question |
|--|---|--|---|
| Adults in intervention arm | 18-99 years old | 73 | 63 |
| Adults in control arm | 18-99 years old | 73 | 63 |
| | | | |
| | | | |
| Total: 146 | | | |

B. Overall Study Sample Size

If this is a multi-site study, provide the total number of subjects to be enrolled from all sites.

Total number of subjects across all sites: 146

C. Eligibility Criteria

1. Identify the criteria for inclusion and exclusion.

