1. Include an explanation of the study design (e.g., randomized placebo-controlled, cross-over, cross-sectional, longitudinal, etc.) and, if appropriate, describe stratification/ randomization/blinding scheme.

Randomized, non-blinded, controlled trial. Patients will be randomized into intervention (specific patient opioid education performed) and control (standard of care without specific patient opioid education) arms through a randomization scheme in REDCap. Randomization will be stratified by medical center (UC Irvine Medical Center versus Kaiser Permanente Orange County – Irvine Medical Center). Patients and providers will not be blinded due to the nature of the intervention (educational).

2. Provide precise definitions of the study endpoints and criteria for evaluation; if the primary outcomes are derived from several measurements (i.e., composite variables) or if endpoints are based composite variables, then describe precisely how the composite variables are derived.

Primary outcome: mean number of opioid tablets consumed 2 weeks postoperatively

Secondary outcome variables:

1. Patient reported opioid consumption 6 weeks postoperatively
2. Modified surgical pain score (validated questionnaire) at the preoperative assessment and 2 weeks and 6 weeks postoperatively
3. Responses to the Preoperative Opioid Education Study Survey (investigator authored) at the preoperative assessment
4. Responses to the Postoperative Opioid Education Study Survey (investigator authored) at 2 weeks and 6 weeks postoperatively
5. Evaluate the number of opioid prescription refills postoperatively within the UC Irvine electronic medical record system and California Department of Justice CURES 2.0 database at 2 weeks, 6 weeks, 12 weeks, and 12 months postoperatively
6. Evaluate intraoperative complications (packed red blood cell transfusion, bowel injury, bladder injury, ureteral injury, conversion to laparotomy) – each variable will be measured independently
7. Evaluate postoperative complications (mesh exposure, wound infection, packed red blood cell transfusion, neuropathy, or urinary tract infection within 6 weeks postoperatively or return to the operating room for within 14 days post operatively) – each variable will be measured independently
8. Total daily morphine equivalents prescribed in the hospital prior to discharge – to be calculated using the Opiate Equianalgesic Dosing Chart
9. Post-operative date upon discharge from the hospital

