During the 2 week postoperative visit, the remaining opioid tablets will be counted and recorded by a co-investigator. The patient will complete the modified surgical pain score and postoperative opioid education study survey. The UC Irvine electronic medical record system and CURES 2.0 Database will be queried to evaluate for additional opioid prescriptions since the time of surgery. Patients randomized to the intervention arm will receive the second opioid informational pamphlet, which will be reviewed by a co-investigator.

During the 6 week postoperative visit, the patient will complete the modified surgical pain score and postoperative opioid education study survey. The UC Irvine electronic medical record system and CURES 2.0 Database will be queried to evaluate for additional opioid prescriptions since the time of surgery. The patients' electronic medical records will be reviewed after the 6 week postoperative visit to evaluate for postoperative complications.

Twelve weeks after the surgery, the UC Irvine electronic medical record system and CURES 2.0 Database will be queried to evaluate for additional opioid prescriptions since the time of surgery.

If a patient fails to follow up for a postoperative visit, at least two attempts will be made to contact the patient via telephone to collect opioid pill counts and have the patient verbally complete the modified

surgical pain score and postoperative opioid education study survey. Initial statistical analysis will be performed after the 12 week postoperative opioid refill assessment

Twelve months after the surgery, the UC Irvine electronic medical record system and CURES 2.0 Database will be queried to evaluate for additional opioid prescriptions since the time of surgery. Additional statistical analysis will be performed after the 12 month opioid refill prescriptions have been evaluated.

While this is a multi-site trial involving subjects from UC Irvine and Kaiser Permanente Orange County – Irvine, only deidentified data will be uploaded into the REDCap data management system. The lead investigator will maintain a separate key containing patient health information for subjects from both sites, which will be utilized to evaluate for additional opioid prescriptions 12 months after the surgery. Co-investigators from both study sites will not have access to identifiable data from subjects that were not recruited from their particular study site.

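### The plan allows the co-investigator who taught the patient to make her 2 week tablet count, the sole primary outcome, and describes the counter in three different ways

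*Combined protocol and SAP*

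**What the plan says.** The primary outcome (Section 1 item 4 and Section 6.B.2) is the mean number of opioid tablets consumed 2 weeks after surgery, compared between arms by a t-test (Section 6.I.2).

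- **Section 6.C.1, 2 week visit:** "the remaining opioid tablets will be counted and recorded by a co-investigator". Pain score, survey and database queries follow, and then the visit's teaching: "Patients randomized to the intervention arm will receive the second opioid informational pamphlet, which will be reviewed by a co-investigator".
- **Research-team entries before Section 3:** the entry for the urogynecology fellow includes "providing standardized patient education about opioid medications, administering patient questionnaires, and quantifying remaining postoperative opioid tablets". The next entry, for a research assistant, lists only questionnaires and counting. That person "is a research assistant within the department of Obstetrics and Gynecology at UC Irvine Medical Center".
- **Non-technical summary:** consumption is assessed by "physician-mediated pill counts during the patients’ standardized postoperative clinic visits".
- **Section 6.B.1:** the trial is non-blinded, and the reason given is "Patients and providers will not be blinded due to the nature of the intervention (educational".

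The visible text does not mention masking of the person who counts.

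**The concern.** Counting tablets in a bottle is close to objective. Arriving at tablets consumed is less so when the bottle was forgotten, tablets are kept elsewhere, or some are said to have been thrown away. The visible text gives no rule for these cases, so someone must decide how far to probe and what to record. Disposal may itself differ by arm, because Section 1 item 3 hypothesises more recommended disposal after education.

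If the person deciding knows the arm, or taught that patient, ambiguous counts may be settled differently in the two arms. A patient may also under-report use to the person who warned her about opioids. Any such difference goes straight into the only primary comparison, where the t-test cannot tell it from an effect of education. The pain score and survey taken at the same visit are exposed in the same way.

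**Working it through.** **1. Who counts, and who teaches**

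| Place | Counter | Teaches? |
|---|---|---|
| Non-technical summary | physician-mediated | not stated |
| Section 6.C.1 | a co-investigator | a co-investigator reviews pamphlet 2 |
| Team entry, fellow | yes | yes |
| Team entry, research assistant | yes | none listed |

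The Section 6.C.1 wording is met if one person does both tasks, and the fellow's entry provides for exactly that. It is equally met if two people do them. The overlap is therefore permitted, not required. The three descriptions of the counter do not match.

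**2. The plan's own sample size**

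Inputs from Section 6.I.5: difference 5 tablets, equal to 0.5 SD, so SD = 5/0.5 = 10; alpha 0.05 (two-sided reproduces the figure, one-sided gives 50); power 80%; 15% attrition.

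n per arm = 2 × (1.960 + 0.842)² × 10²/5² = 62.8, rounded up to **63**, as stated (power 80.1% by the normal approximation). Completers from 73 recruited: 73 × 0.85 = 62.05, about 62.

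**3. Illustration of a recording shift**

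The documents give no figure for such a shift, so each value b below is an assumption. With no true effect and a mean between-arm recording difference of b tablets:

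- SE = 10 × √(2/63) = 1.78 tablets (1.80 with 62 per arm)
- P(reject) = Φ(b/SE − 1.96) + Φ(−b/SE − 1.96)

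| b (tablets) | Share of 5-tablet target | Normal approximation, n = 63 | t-test, n = 62 |
|---|---|---|---|
| 0 | 0% | 5.0% | 5.0% |
| 0.2 | 4% | 5.1% | 5.1% |
| 0.5 | 10% | 5.9% | 5.9% |
| 1 | 20% | 8.7% | 8.6% |
| 2 | 40% | 20.2% | 19.7% |

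**4. What the shifts would require**

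Mean shift = fraction of counts affected × average error in each. If 10% of one arm's counts are ambiguous and each moves by 2 tablets, b = 0.10 × 2 = 0.2. Reaching b = 1 with the same 10% needs an error of 10 tablets in each affected patient, which is as large as the whole control mean the plan anticipates.

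**The case against.** **The overlap is not stated.** A reader might infer that the counter necessarily knows the arm. The text does not support that. The counter and the teacher may be different people, and control patients receive no pamphlet at that visit. What stands is that nothing prevents the overlap.

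**The order is already right.** Section 6.C.1 is a chronological account and puts the count and questionnaires before pamphlet 2. That is the natural reading, so the order needs only to be made explicit. It does not mask a counter who gave the first pamphlet before surgery or who can see the allocation.

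**The trial is declared non-blinded.** A co-investigator who treats the patient could be called a provider. But the stated reason is the educational nature of the intervention. It explains why patients and teachers cannot be masked, and does not extend to a person who only counts.

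**A bottle count is largely objective, and patients are telephoned beforehand to bring the bottle.** This stands. It makes the upper rows of the table more plausible than the lower ones.

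**A masked counter may not be available.** This stands in part. The research assistant is described only as UC Irvine staff, and Section 6.C.1 keeps co-investigators from identifiable data of the other site's subjects. Some personnel pages are not in the text reviewed, and the tick-boxes for recruiting and consenting in the assistant's entry cannot be read. Having no listed teaching duty does not prove that the assistant is unaware of allocation. It would be wrong to infer that the change needs no extra staff at both sites.

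**Masking leaves part of the problem.** This also stands. Patients may reveal their arm, telephone counts remain patient-supplied, and a masked counter still needs some rule for a forgotten bottle.

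**Conclusion.** The concern holds in limited form. The plan permits one unblinded co-investigator to teach a patient and then make her primary-outcome count, gives no reason for leaving the counter unmasked, and describes the counter inconsistently. At UC Irvine the means of separating the two tasks are already in the team list.

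The size is unknown. The range of about 5.1% to 20% rests on the plan's SD of 10, on 62 to 63 completers per arm, and on an assumed mean shift of 0.2 to 2 tablets between whole arms. The lower end is the more realistic. A reader might take the 20% as an estimate of the trial's error rate, but the documents give nothing from which to estimate one. The case for acting is that the exposure falls on the sole primary outcome and is cheap to reduce, not that a large bias has been shown.

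**What to change.** - **Reconcile the counter.** Amend the Non-technical summary and Section 6.C.1 to agree with the team entries on who counts.
- **UC Irvine.** State that the 2 week count and questionnaires are done by the research assistant already listed for them, without access to the REDCap allocation and with no part in consenting, randomising or teaching that patient.
- **Order.** Say outright that the count and questionnaires come before pamphlet 2.
- **Kaiser and telephone counts.** Use an already delegated team member who did not teach that patient, where one exists. The visible documents do not show whether one does, so the investigator should name that person or state that none is available.

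The cost is some scheduling effort, a restricted REDCap view and the text amendments. No new staff are needed at UC Irvine if the assistant can be kept out of consent and randomisation; Kaiser cannot be judged from the text. Sample size, alpha and the analysis do not change. Patients remain unblinded and may disclose their arm, so the risk of bias is lowered, not eliminated.

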The pattern of postoperative opioid consumption will be evaluated at 2 weeks and 6 weeks after the surgery and will be compared between subjects who underwent preoperative opioid education versus those who did not. The hypothesis is that subjects who receive the preoperative opioid education will be less likely to consume opioid tablets after 2 weeks compared to subjects who did not receive the educational intervention.

The rates of prescription refills 12 months after the surgery will be evaluated and compared between subjects who underwent preoperative opioid education versus those who did not. The hypothesis is that subjects who receive preoperative opioid education will be less likely to have opioid refills within the first 12 months postoperatively compared to subjects who did not receive the educational intervention.

The postoperative opioid consumption between subjects with particular clinical conditions (preoperative opioid use, active tobacco use, the presence of a chronic pain syndrome, anxiety, depression) will be compared to subjects without these conditions. The hypothesis is that subjects with these clinical conditions will have higher postoperative opioid consumption rates, including higher rates of opioid prescription refills within 12 months after surgery, compared to subjects without these conditions.

The subjects' opinions about the adequacy of their initial postoperative opioid prescriptions will be compared between subjects who received the preoperative educational intervention versus those who did not. The hypothesis is that subjects who received the preoperative educational intervention will be more likely to answer that their opioid prescription was "more than adequate" or "adequate" compared to subjects who did not receive the educational intervention. The subjects' opinions regarding the adequacy of their initial postoperative opioid prescriptions will be compared between subjects with particular clinical conditions (chronic pain syndromes, anxiety, depression, active tobacco use, and preoperative opioid use) to subjects without these conditions. The hypothesis is that subjects with the clinical conditions will be more likely to answer "less than adequate" regarding their postoperative opioid prescriptions compared to subjects without these clinical conditions.

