10. Post-operative date that the patient passed a voiding trial and the transurethral catheter was removed
11. Duration of the surgery (in minutes)

C. Research Procedures

1. Provide a detailed chronological description of all research procedures.

The study concept would be introduced to the patients at the consult visit, preoperative visit, on in the preoperative unit prior to surgery. If the patient agrees to participation during any of these encounters, written consent and HIPPA authorization will be obtained and the patient would be randomized to the intervention or control arm using a computerized randomization scheme on REDCap. The randomization will be stratified by the site of the surgery (UC Irvine Medical Center versus Kaiser Permanente Orange County – Irvine Medical Center). If the patient is randomized to the intervention arm, the first opioid informational pamphlet will be provided and reviewed with the patient in addition to standard preoperative instructions. If the patient is randomized to the control arm, standard preoperative instructions will be provided. Patients within both arms of the study will receive standardized postoperative medication prescriptions prior to the surgery. Patients within both arms of the study will complete the modified surgical pain score and preoperative opioid education study survey prior to surgery.

After the surgery is completed, the primary surgeon will decide whether to admit the patient to the hospital and which postoperative analgesics will be administered within the hospital prior to discharge for subjects in both study arms. The patient will follow up for standard postoperative clinic visits at 2 weeks and 6 weeks postoperatively. One to two days prior to the 2 week postoperative visit, the patient will be contacted via telephone to remind her to bring her opioid prescription bottle to the clinic visit.

Between the surgery date and the 2 week postoperative visit, the electronic medical records will be reviewed to evaluate the length of the surgery, intraoperative complications, the postoperative date of discharge, the postoperative date of removal of the transurethral foley catheter, the total daily morphine equivalents that the patient was prescribed prior to discharge from the hospital, and the presence of opioid prescriptions 30 days prior to the surgery. Additionally, the CURES 2.0 Database will be queried to evaluate for opioid prescriptions 30 days prior to the surgery.

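### The refill outcome counts any opioid prescription after surgery and does not separate therapy already under way, which favours the preoperative-user hypothesis and dilutes the comparison between arms.

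*Combined protocol and SAP*

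**What the plan says.** **The outcome.** Secondary outcome 5 (Section 1 item 4, repeated in Section 6.B item 2) reads "Evaluate the number of opioid prescription refills postoperatively within the UC Irvine electronic medical record system and California Department of Justice CURES 2.0 database", assessed at 2, 6 and 12 weeks and 12 months. Section 6.B item 2 is where the form asks for precise endpoint definitions, but refill is not defined there or elsewhere.

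**The measuring rule.** In Section 6.C item 1, each follow-up query is described in the same way: the UC Irvine record and "CURES 2.0 Database will be queried to evaluate for additional opioid prescriptions since the time of surgery". The non-technical summary is as broad: "Any additional opioid prescriptions within 12 months of the surgery will be evaluated". Section 6.C item 1 then refers to the 12-week query as the assessment of refills, so the plan treats the two as the same thing. No limit by prescriber, indication or continuation of earlier therapy is stated.

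**Preoperative users.** The exclusion criteria (Section 3.C) do not remove them. Section 6.C item 1 collects their data from the medical record and adds that "the CURES 2.0 Database will be queried to evaluate for opioid prescriptions 30 days prior to the surgery". Section 1 item 3 lists the conditions to be compared as "preoperative opioid use, active tobacco use, the presence of a chronic pain syndrome, anxiety, depression" and predicts greater consumption in patients who have them, "including higher rates of opioid prescription refills within 12 months after surgery, compared to subjects without these conditions".

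**The analysis.** Section 6.I item 3 gives an unadjusted Mann-Whitney test of the refill count between arms. It names no method for the condition comparisons, and nothing says that the 30-day data will filter, adjust or stratify the refill count.

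**The concern.** A patient on a continuing opioid regimen has a prescription before surgery and more after it. The first can place her in the preoperative-use group, and the later ones count as her refills. Both come from the same two sources. A positive result for the refill part of the hypothesis therefore cannot separate extra need after surgery from continuation of what was there before.

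The randomised comparison is affected in another way. Patients who continue long-term therapy take the top ranks of the Mann-Whitney test whichever arm they are in. They add noise to the contrast that the education is meant to change, and the effect grows with follow-up because continuing prescriptions accumulate over 12 weeks and 12 months.

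**Working it through.** **1. The plan's own calculation.** Section 6.I item 5 gives 63 per arm for a difference of 5 tablets equal to 0.5 SD, so the SD is 10. With two-sided alpha 0.05 and 80% power, n = 2 × (1.96 + 0.84)² × (10/5)² = 2 × 7.84 × 4 = 62.7, so 63. The figure reproduces. It concerns tablets at 2 weeks only; the documents give no rate, effect size or power for refills. Everything below rests on assumed rates.

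**2. Preoperative users against non-users.** Inputs:
- 126 patients (63 per arm, Section 6.I item 5).
- Users at 5%, 10% and 20%, that is 6, 13 and 25 patients (assumed).
- Surgery-related refill probability 15% in both groups, so there is no true difference (assumed).
- Users who continue therapy fill a Poisson number of prescriptions with mean 12 over 12 months (assumed).
- Two-sided Mann-Whitney at 0.05 (assumed, since the plan names no test here).

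Share of 3,000 simulated trials that are significant, by the fraction of users who continue:

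| Users of 126 | none | 25% | 50% | 80% | all |
|---|---|---|---|---|---|
| 6 | 4% | 39% | 78% | 99% | 100% |
| 13 | 3% | 58% | 96% | 100% | 100% |
| 25 | 5% | 77% | 100% | 100% | 100% |

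The first column is also the result if continuing prescriptions are left out of the count. A second, independent set of runs gave about 4%, 40–75% and 81–100% for none, 25% and 50% continuing. The sets agree within about three points. With any refill versus none and Fisher's exact test, the ranges are 2–4%, 22–60% and 58–99%.

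**3. Between arms, type I error.** With 15% surgery-related refills in both arms and 0% to 30% of patients having continuing fills, the Mann-Whitney test rejected in 4.7% to 5.2% of 3,000 runs. There is no bias.

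**4. Between arms, power.** Assumed true refill rates are 25% (control) and 8% (education), with a fraction f of long-term users in each arm who each fill about 12 prescriptions. A normal approximation shows the mechanism:
- Signal, P(control higher) + ½P(tie) − ½: about (1 − f)² × (0.25 − 0.08)/2 = 0.085 × (1 − f)², because only pairs of two non-users carry much information.
- Tie factor: T = 1 − [0.835(1 − f)]³ − [0.165(1 − f)]³, where 0.165 is the mean of the two rates. Ties among long-term users are ignored.
- SE = √(127/(12 × 63 × 63) × T) = √(0.002667 × T).
- Power ≈ Φ(signal/SE − 1.96).

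| f | Signal | T | SE | Approximate power | Simulated power, all patients | Simulated power, non-users only |
|---|---|---|---|---|---|---|
| 0 | 0.0850 | 0.413 | 0.0332 | 73% | 74% | 74% |
| 5% | 0.0767 | 0.497 | 0.0364 | 56% | 58% | 73% |
| 10% | 0.0689 | 0.572 | 0.0391 | 42% | 42% | 71% |
| 20% | 0.0544 | 0.700 | 0.0432 | 24% | 25% | 66% |

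The signal shrinks and the standard error grows together. Restricting to non-users loses only sample size: at f = 20%, 63 × 0.8 = about 50 per arm remain.

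**The case against.** **A query is not a scoring rule.** The listed outcome says refills, and the word additional could carry an implied limit. That would leave an undefined term and no stated rule to count every prescription. In part this stands: a reader might infer that the plan expressly scores prescriptions for an injury or dental work as refills, and no sentence says so. But the non-technical summary and Section 6.C use the same broad wording, Section 6.C treats the query as the refill assessment, and no narrower rule exists. Followed as written, the plan produces the broad count.

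**The hypothesis is not settled in advance.** A reader might infer that it is confirmed by construction. The documents do not support that. One short course within 30 days makes a patient a preoperative user and does not guarantee a later prescription. Certain rejection requires nearly all users to continue, and the documents give no continuation rate. If none continue, there is no inflation.

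**The randomised comparison remains valid.** A reader might infer bias between arms. Randomisation balances continuing users in expectation, and the type I error is nominal. The loss is power, on one of eleven secondary outcomes for which the trial claims none. The power figures also assume that education leaves long-term prescribing unchanged.

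**Total prescribing is a legitimate outcome, and the aim is not causal.** Both statements are fair. Section 1 item 3 predicts higher rates in users and does not say that surgery causes them. This is a reason to keep the all-prescription count, but not to let it stand alone under the name of refills.

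**Classifying prescriptions by indication may not be simple.** This stands. The documents do not say that CURES records an indication, staff are not blinded (Section 6.B item 1), and patients are not contacted after week 6 (Section 6.C item 2).

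**Conclusion.** The concern holds in a limited form. The operational count does not separate continuing therapy, and the 30-day data that would allow this are collected but not used in the refill analysis.

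- **Preoperative-user hypothesis, refill part only:** strongly favoured by the definition. The size depends mainly on the unknown continuation rate: a quarter of users continuing is enough to raise the rejection rate from about 4% to 40% or more under the assumptions shown. Tablet consumption and the primary outcome are not touched.
- **Comparison between arms:** no bias, but dilution. At an assumed 10% of long-term users, power falls by 32 points (74% to 42%), and analysing non-users recovers 29 of them (71%).

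The direction of both effects follows from the definition. The sizes rest on assumed refill rates, prevalence and 12 fills a year. The plan should be changed, but the primary analysis is not at risk.

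**What to change.** 1. Keep the count of all opioid prescriptions, and name it as total opioid prescribing after surgery.
2. Add to Section 6.I item 3 a comparison of refills between arms, at each time point and above all at 12 weeks and 12 months, among patients with no opioid prescription in the 30 days before surgery. A test stratified by preoperative use is an alternative.
3. Define preoperative use so that the study's own postoperative prescription is excluded from the look-back. Section 6.C item 1 has it issued before surgery in both arms, so otherwise it could label patients who were not taking opioids as users.
4. Drop the refill part of the Section 1 item 3 hypothesis for preoperative users, or report it only as a description of total prescribing that includes continuing therapy.
5. Optionally, as a supportive analysis, classify prescriptions by indication where the record gives one, without knowledge of arm and with an unknown category.

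Items 1 to 4 need a few lines of text and no new data. The cost is a somewhat smaller sample in the restricted analysis (about 57 per arm at 10% users, 63 × 0.9), which does not describe preoperative users. Item 5 takes abstraction effort and may leave many prescriptions unknown.
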